Clinician, Practice and Network level CRC screening rates: We will use established, validated algorithms for calculating cancer screening rates using a combination of administrative, billing and clinical data. [name] (co-l) led the algorithm development efforts at MGH and Partners, and he will work with the MMC team to ensure CRC screening rates are comparable across sites. Data is aggregated at the physician, practice and network (e.g. MGH, MMC, PCPO) level to identify the percentage of eligible patients up to date for screening during the historical control period, and concurrent observation period for study and non-study clinicians. Limited data on patient characteristics (e.g. age, gender, education, insurance status, etc) will be collected along with screening rates.

Clinician reported measures: clinicians will complete a baseline survey and a telephonebased simulated patient interaction (SPI) before staff start enrolling their patients onto the trial. They will complete a short survey after each eligible patient visit. After patient enrollment is complete, all clinicians will participate in a debrief interview.

- **Baseline clinician survey** will include the same CRC knowledge items as the patients and 3 items to assess clinicians' confidence in their ability to present benefits and harms, to discuss probabilities of benefits and harms and to elicit patients' goals and concerns during an office visit, each based on a five-point scale (not at all, a little, somewhat, very, and extremely confident).
- **Post visit survey:** 4 items SDMP survey will be adapted for use by clinicians, time spent discussing CRC screening in visit, recommendation, patient's preferred approach, and satisfaction with visit.

- **Baseline SDM skills assessment:** The telephone-based SPI will be transcribed and coded by two trained coders according to the well-validated Braddock's Informed Decision Making framework. The Braddock framework covers the core areas of SDM skills. ^{x,xi} A total score 0-9 will be calculated with higher scores indicating more SDM skills.

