- **Debrief interview and survey**: After patient recruitment is complete, study staff will conduct a brief interview with all participating clinicians and will follow a structured interview guide to assess clinicians' attitudes toward SDM, their perceptions of the study and satisfaction with the intervention, and ideas for improvement. The clinicians will also be asked to complete a short, online survey to re-assess their confidence in their ability to present benefits and harms, to discuss probabilities of benefits and harms and to elicit patients' goals and concerns during an office visit.

Caregiver measures: a short survey post visit will contain SDMP survey, their perception of physician recommendation, their preferred approach to screening and their perception of the patient's preference for screening.

Adherence to intervention(s): The online training platform will track completion of modules and time spent on the webinar. Staff will track completion rates and time for the SPIs, delivery of the registry reports, participation in monthly case discussion sessions, and documentation in notes of CRC screening discussions in order to examine whether outcomes are affected by adherence to the protocol.

Patients will self-report time spent discussing CRC screening in the visit. Finally, staff will conduct a short follow-up survey with a subset of patients at 12 months to confirm screening choice and reasons for any discrepancy between preferred and implemented approach (e.g. transportation, insurance, clinician recommendation, spouse/caregiver preference, other new or worsening illness).

All study staff are Collaborative Institutional Training Initiative (CITI) certified and will receive training from the PI and program manager in the study protocol. We will hold regular meetings to review screening, enrollment and completion data, to discuss protocol and standard operating procedures, and to identify and mitigate any issues that arise.

For studies involving treatment or diagnosis, provide information about standard of care at Partners (e.g., BWH, MGH) and indicate how the study procedures differ from standard care. Provide information on available alternative treatments, procedures, or methods of diagnosis.

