Investigators at each site will identify clinicians with a high volume of patients aged 76-85 and those who see patients at community health centers or centers with higher patient diversity. The recruitment and study procedure for clinicians is as follows:

- The PIs and co-investigators will inform clinicians about the study and invite their participation in multiple ways: through presentations at clinical leadership meetings, practice meetings, through HDSC newsletter, through Partners Center for Population Health Newsletter, and through calls, meetings and emails to individual clinicians. Reminder emails will be conducted for non-responders within 2 weeks of the initial outreach.
- 2. Clinicians will indicate interest in participating in the study by contacting the PIs or study staff (either via email, phone or in person).
- 3. Study staff will contact interested clinicians to collect information to confirm eligibility and to support randomization using the screener questionnaire and will send an information sheet to clinicians that details the requirements of the study.
- 4. Clinicians will indicate their consent to participate by sending an email with their intention to join the study.
- 5. Study staff will then run an RPDR report to identify the clinicians' eligible patients due for colorectal cancer screening in the study year.
- 6. Eligible Clinicians will be randomly assigned to an arm by study statistician.
- 7. Clinicians assigned to the registry arm will have 4 weeks to complete:
 - a. Baseline survey via RedCap or phone
 - b. A telephone-based SPI conducted with standardized patients that will be audiotaped
 - c. Short meeting with staff to review protocol and preferences for receiving the registry information about potentially eligible patients (e.g. 24h in advance of visit, weekly report, at morning huddle through medical asst)
 - d. Review of their eligible patient list to indicate any patient that should not be approached for the study and a reason for exclusion.
 - e. Study staff will send up to six reminder emails for each activity and make two reminder calls to encourage completion of each activity.
- 8. Clinicians assigned to the SDM training arm will have 4 weeks to complete:
 - a. Baseline survey via RedCap or phone
 - b. The online training course
 - c. A telephone-based interaction conducted with a standardized patient. Study staff will email feedback 1 week after completion.

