 - d. Short meeting with staff to review protocol and preferences for receiving the information about potentially eligible patients (e.g. 24h in advance of visit, weekly report, at morning huddle through medical asst)
 - e. Review of their eligible patient list to indicate any patient that should not be approached for the study and a reason for exclusion.
 - f. Study staff will send up to six reminder emails for each activity and make two reminder calls to encourage completion of each activity.
- 9. Clinicians in the SDM Training arm will complete a second SPI about 8-12 weeks after the first and will have the opportunity to participate in monthly 'office hours' sessions conference calls open to all participants in this arm that will be facilitated by SDM experts, primary care physicians and/or a gastroenterologist, to discuss cases and field questions and challenges that come up as they put the skills into practice.
- 10. After each eligible patient visit, staff will email a short questionnaire to participating clinicians. Staff will follow up with two reminder emails at 24 and 48 hours to complete the questions.
- 11. After patient enrollment is complete, staff will schedule an exit interview with clinicians. For participants who are not able to attend in person, the interview will be conducted by phone.

Patient and caregiver recruitment:

- 1. Study staff will review clinic schedules and medical records to identify eligible patients for participating clinicians prior to their scheduled visit. An Epic Report will be created to assist with this screening and eligibility review.
- 2. About two weeks before the visit, the research coordinator will send a cover letter signed by the participating clinician and an information sheet describing the study to all eligible patients. The cover letter will have information for participants who wish to opt out of the survey. Eligible patients at Maine Medical Center will also receive a post-card they may send back to opt-out of the study.

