### Physician Outcomes:

Physicians completed short background and baseline surveys to collect demographics and prior SDM training experience. They were also asked to review a list of their patients before being randomized into the study. Further, physicians completed a telephone-based SPI before staff started to enroll their patients. Lastly, once patient enrollment was complete, all physicians participated in a debrief interview.

- Background physician survey: Items assessed the number of years the physician had been in clinical practice, years working at their current site, and clinical sessions each week, as well as age, race, ethnicity, specialty, gender, and contact information. Additionally, physicians reported any prior formal training in SDM (and defined what that experience was).
- Baseline physician survey: Items assessed attitudes towards colonoscopy, stool-based tests, and not screening patients in this age group, subjective norms, and behavioral intention to engage their older adults in decisions about CRC screening. Physicians also completed the knowledge items and the physician's reactions to uncertainty scale.
- Simulated patient interaction: Physicians in both arms completed a telephone-based SPI before patient enrollment started. Intervention arm physicians complete the SPI after the SDM training. The SPIs were audio recorded and professionally transcribed, de-identified, and coded by two trained coders, who were blinded to the physicians' assignment. Coding followed the well-validated Braddock's Informed Decision Making framework to assess for presence of SDM elements.
- Post-visit survey: Physician participants completed a short online survey via REDCap after each eligible patient visit. The survey contained the SDM Process items adapted for physicians as well as an opportunity to provide a reason for not discussing CRC screening.

• Debrief interview: After patient recruitment was complete, research staff conducted a brief interview with participating physicians that followed a structured interview guide to assess physicians' attitudes toward SDM, their perceptions of the study, and satisfaction with the intervention, and ideas for improvement.

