*Sample Size*: The study was powered to detect a small to medium effect size difference in the primary outcome, SDM process score. With 500 surveys (250 per arm), assuming an intraclass correlation coefficient of 0.03, the effective patient sample size was estimated at 394, which would enable detection of a difference of 0.28 standard deviations with 80% power and a two-sided significance level of 0.05.

*Statistical methods*: Responders and non-responders were compared to examine potential non-response bias using two-sample t-tests or chi-square tests. Patient sample characteristics were compared between arms using two-sample t-tests or chi-square tests. Multivariable regression models were used to adjust for potential effects of any unbalanced variables.

The following hypotheses were evaluated using an intention to treat approach, and patient outcomes were analyzed based on their physicians' assigned arm regardless of whether the physician completed the training, received the reminder, or discussed CRC screening.

 Examine the effects of the interventions on patients' SDM Process scores and knowledge score:

- a. Compared to the Comparator group, patients seen by physicians in the Intervention arm would report higher SDM Process scores (primary outcome) : We will examine the distribution of the SDM Process score and apply variable transformation techniques if necessary. We will use linear regression models with the Generalized Estimating Equations (GEE) techniques to account for the patients within clinician data structure. We will be able to difference of 0.28 SD for the SDM Process score with 80% power. Studies using the SDM Process survey have found effect sizes ranging from 0.39SD – 0.88SD when comparing sites that used have formal decision support (coaching or decision aids) and those that did not. Although we have sufficient power to detect a smaller difference, we are interested in a meaningful difference 0.4SD or higher.

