  - a. Compared to the Comparator group, physicians in the Intervention arm will report higher confidence in their SDM skills: Clinician confidence will first be analyzed as a continuous variable. Variable transformation will be performed to improve normality assumption if deemed necessary. Additionally, we will dichotomize the

variable into very or extremely confident vs. not. A two-sample t-test or Wilcoxon rank sum test, as appropriate, will be used to compare the continuous outcome while a chi square test will be used to compare the dichotomized outcome. With a sample size of 50 clinicians, we will have 81% power to detect difference of 35%, e.g. from 50% to 85%, in the percentage of clinicians who are very or extremely confident in different elements needed to conduct SDM conversations. In our prior study of the SDM skills webinar, we found a 30-40% absolute increase in clinician confidence.

- b. Compared to the Comparator group, physicians in the Intervention arm will demonstrate more SDM skills in the SPI: We will code each transcript using Braddock's Informed Decision Making framework that covers core aspects of SDM (scores range from 0 to 9). First, we will determine whether a two-sample t-test or a Wilcoxon rank sum test is more appropriate to compare the two groups. Assuming the score is normally distributed, a sample size of 25 in each group will have 80% power to detect a 0.81SD difference in the mean Braddock score (or about 1.4 points out of 9). Our prior study of a 3-hour CME online SDM skills webinar, we found an increase of 1.2SD on the Braddock scale after training.
- c. Compared to the Comparator group, physicians in the Intervention arm will report higher satisfaction with the visit. The percentage of clinicians who report that they are extremely satisfied with the visit will be compared across arms using a chisquare test.
- 4. Examine the effects of the interventions on **caregivers' SDM Process scores**: Caregivers who attended a visit with an eligible patient (and for whom the patient provided contact

information) were invited to complete a post-visit survey. They were asked to complete an adapted version of the SDM Process survey to provide their perspective on the conversation and involvement of the patient. A total score will range from 0-4, with higher scores indicating more shared decision making. These analyses are exploratory.

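### SAP hypothesis 3a does not use the baseline confidence score that the protocol plans to collect; the planned tests are valid, but precision is given up

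*SAP*

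**What the plan says.** **Measurement.** In the protocol, the baseline clinician survey has three items on a five-point scale, covering clinicians' "confidence in their ability to present benefits and harms, to discuss probabilities of benefits and harms and to elicit" patients' goals. After patient recruitment the protocol adds an exit measurement: "The clinicians will also be asked to complete a short, online survey to re-assess their confidence in their ability to present benefits and harms", with the other two topics repeated as well.

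**Analysis.** Under Statistical methods, hypothesis 3a, the SAP states: "A two-sample t-test or Wilcoxon rank sum test, as appropriate, will be used to compare the continuous outcome". Confidence is also dichotomised (very or extremely confident, or not) and compared by chi-square. Neither test has a baseline term. The stated power is 81% for 50% against 85% with 50 clinicians, and it refers to the dichotomised outcome only.

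**Adjustment elsewhere.** The SAP's one general sentence is "Multivariable regression models were used to adjust for potential effects of any unbalanced variables". It directly follows the comparison of patient characteristics and does not name baseline confidence.

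**Timing.** In the protocol's clinician recruitment steps, randomisation is step 6. Step 8 then begins "Clinicians assigned to the SDM training arm will have 4 weeks to complete" and lists the baseline survey and the online course in the same window, with no required order. Among the tasks of that window is "Review of their eligible patient list to indicate any patient that should not be approached for the study". The SAP's Physician Outcomes section mentions the baseline survey and then says of the list review: "They were also asked to review a list of their patients before being randomized into the study". The two documents therefore disagree on where the list review falls relative to randomisation.

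**The concern.** A before-and-after measure is planned and its before-value goes unused, in the smallest analysis set of the trial (about 50 clinicians). Randomisation makes an unadjusted comparison sound, but a baseline value of the same scale usually explains part of the variation at exit. Leaving it out gives a wider interval than the collected data would allow.

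The stake is limited. Confidence is a hypothesis under Aim 3; the protocol's primary outcome is patient-reported SDM, and its key secondary outcomes concern patients' knowledge and preference-tailored decisions. What could be gained is a sharper answer to 3a at almost no cost, provided that the baseline score really is a baseline.

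**Working it through.** **Inputs**
- 50 clinicians and the rates 50% and 85%: SAP 3a.
- 25 per arm: stated in SAP 3b, taken to apply to 3a.
- Two-sided 0.05: stated for the primary outcome, assumed for 3a.
- Baseline-to-exit correlation r: not in the documents, so a range is shown.

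**1. The plan's own figures.** Two-proportion z-test with unpooled variance: SE = sqrt(0.50×0.50/25 + 0.85×0.15/25) = 0.1229; 0.35/0.1229 = 2.848; 2.848 − 1.960 = 0.888; power 81.3%, against 81% stated. Exact enumeration of the uncorrected chi-square gives 79.0%. For a t-test with 25 per arm (48 df, noncentral t), the detectable difference at 80% power is 0.809 SD, which matches the 0.81 SD given in 3b.

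**2. Continuous score with baseline adjustment.** The variance relative to the unadjusted test is g = (1 − r²) × (2n − 3)/(2n − 4); the second factor is the cost of estimating the slope. With n = 25 it is 47/46, and the test has 47 df.

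| r | g | Detectable difference | Power at 0.81 SD |
|---|---|---|---|
| none (unadjusted) | 1 | 0.81 SD | 80% |
| 0.1 | 1.012 | 0.81 SD | 79.5% |
| 0.2 | 0.981 | 0.80 SD | 80.7% |
| 0.3 | 0.930 | 0.78 SD | 82.7% |
| 0.5 | 0.766 | 0.71 SD | 89.2% |

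The detectable differences for "unadjusted" and r = 0.1 are 0.809 and 0.814 SD before rounding. Break-even lies at r of about 0.15 (0.17 with 20 per arm, 0.13 to 0.14 with 30). At r = 0.5 the gain is equivalent to 50/0.766 = about 65 clinicians.

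**3. Dichotomised outcome.** Simulations (latent-normal model, 50% against 85%, 25 per arm) compared the chi-square test with a baseline-adjusted logistic model. Power rose from about 79% to 81-82% at r = 0.3 and to 85-86% at r = 0.5. The variance of an adjusted risk difference fell by about 3% and 13%, less than the 7% and 23% for the continuous score. A linear model of the binary outcome was less favourable: 81% to 84% at r = 0.5 and almost no gain at 0.3 or below.

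**4. If knowing the arm shifts the baseline.** The adjusted estimate is the exit difference minus slope × baseline difference, and in SD units the slope is about r. Suppose that knowing the assignment raises SDM-arm baseline scores by 0.2 SD (assumed) and leaves exit scores unchanged. The bias is then −0.2r: −0.04, −0.06 and −0.10 SD at r = 0.2, 0.3 and 0.5. In simulation (20,000 runs, true difference 0.81 SD), power is about 76%, 76% and 80%, so the gain disappears.

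**5. What r might be.** Per the SAP, physicians enrolled from May to August 2019 and patient enrolment ended in April 2021. The two surveys are therefore roughly 20 months or more apart, and r = 0.5 may be optimistic.

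**The case against.** The strongest case for leaving 3a alone has four parts.

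- **The baseline may not be a clean one.** The protocol gives the survey to clinicians who have already been assigned, so they may know their arm. A date before training does not make the score a pre-randomisation score. This stands, and it decides when the adjusted model may lead. It also rules out any model that forces equal baseline means in the two arms.
- **Results may already be known.** The SAP is dated July 2022, more than a year after patient enrolment ended, and says "The following hypotheses were evaluated using an intention to treat approach". Hypothesis 3a itself is in the future tense, so the documents do not settle this. If 3a has been seen, the planned tests must stay as main.
- **Stratification covers part of it.** Randomisation was stratified by prior SDM training, a plausible correlate of confidence. That helps balance, but the planned tests use neither the strata nor the baseline score, so it does not recover the precision.
- **The gain may be negligible.** True if r is about 0.2 or lower. The documents give no r, so neither a small nor a large gain can be asserted.

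A reader might infer more than the documents support:

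- *That the planned comparison is biased.* It is not. It compares randomised clinicians; the one reservation is that the uncorrected chi-square at 25 per arm has an exact type I error of 6.5% at a common rate of 50%.
- *That confidence was never collected,* because the SAP's physician survey lists do not mention it. Those lists are abridged: they also omit visit satisfaction, which 3c analyses, and the SAP refers to the protocol for methods.
- *That baselines were completed after training.* The documents leave the order open; they do not show this.

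**Conclusion.** The point holds as an optional gain in precision. SAP 3a leaves out a baseline score that the protocol plans to collect, and the planned tests remain valid. Adjustment would bring the detectable difference from 0.81 SD to between 0.80 and 0.71 SD for correlations of 0.2 to 0.5, with a slight loss below about 0.15. The dichotomised outcome can gain too, by less.

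These figures rest on 25 clinicians per arm, two-sided 0.05 and assumed correlations; the results for the dichotomised outcome also rest on a latent-normal model. The benefit depends on the baseline being unaffected by training and by knowledge of the arm, which the protocol's step order and the SAP's account do not establish.

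**What to change.** 1. Check each baseline survey date against the clinician's randomisation date and, in the SDM arm, against the training-platform record.
2. Add to 3a a linear regression of the exit confidence score on arm and baseline confidence, and a baseline-adjusted model for the dichotomised outcome. Report the planned t-test or Wilcoxon test and the chi-square test alongside.
3. Make the adjusted analysis the main one only if baselines were completed before training and, preferably, before clinicians knew their arm. Otherwise, or if 3a results have already been seen, keep the planned tests as main and label the adjusted models as supplementary.
4. State in 3a that the outcome comes from the exit survey and how the three items form the score. Reconcile the two documents on whether the list review came before or after randomisation, and state when the baseline survey was completed.

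The cost is some SAP wording, two regression models and about 50 date checks. Two downsides should be stated: a slight loss of precision at very low correlation, and a possible bias of about −0.04 to −0.10 SD under the assumed 0.2 SD shift from knowing the arm.
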